5.2 Primary outcome measure

DHb (pre-intervention Hb – post-intervention Hb)

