6.1 Study design

Prospective interventional quasi-experimental pre-post study across multiple hospitals in South Africa. Patients will be screened for trial eligibility at a normal routine outpatient clinic visit. Those patients with a screening Hb meeting the criteria for anaemia according to the WHO definition³⁰ and able to receive the oral iron for a minimum of 6 weeks prior to their planned operation, will be eligible for inclusion.

The formal laboratory blood test results will be reviewed within 48-76 hours by the research nurse to diagnose those patients who meet the pre-defined criteria for IDA. Parents & legal guardians will be contacted via telephone by the research nurse to inform them about their child's results and to instruct them to either discontinue or continue taking the oral iron supplementation dependent on whether the results meet the pre-defined criteria for iron-deficiency anaemia.

Prior to inclusion, freely given written informed consent must be obtained from all parents or legal guardians and assent from patients where appropriate.

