5.10 Power analyses

What effect size could we expect to find statistically significant for the whole cohort given an estimated sample size of 176 patients?

Effect size for comparison between mean Hb pre and post intervention for whole cohort (matched pairs samples t-test) of 176 patients. Assuming data are normally distributed.

Sample size = 176, power = 80%, two-tailed significance 0.05

Effect size ~ 0.21

```
pwr.t.test(n = 176, d = NULL, sig.level = 0.05, power = 0.8,
type = "paired", alternative = "two.sided")
```

Paired t test power calculation

n = 176
d = 0.2123609
sig.level = 0.05
power = 0.8
alternative = two.sided

NOTE: n is number of *pairs*

What effect size could we expect to find statistically significant for the cohort of patients with IDA given an estimated sample size of 176 anaemic patients, if the incidence of IDA is unknown?**

IDA prevalence	IDA Sample size	Effect size (matched pairs samples t-test)	Effect size (Wilcoxon signed-rank test (matched pairs))
0,2	35	~0.5	~0.5
0,3	53	~0.4	~0.4
0,4	70	~0.34	~0.35
0,5	88	~0.3	~0.31

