5.11 Statistical analysis

Categorical variables will be reported as number and percentage. All patient and surgical characteristics will be compared between children with and without anaemia and comparing children with IDA versus anaemia of other cause using Pearson's chi-squared or Fisher's exact tests as appropriate. These will include age groups, sex, type of surgery (general, orthopaedic, ENT, plastics, other), severity of surgery as per SAPSOS definitions (mild, moderate, severe), severity of anaemia as per WHO definitions (mild, moderate, severe).

Normal distribution of continuous variables will be determined by Shapiro-Wilk testing and summarised appropriately as means \pm standard deviation or as medians \pm interquartile range (IQR). All patient and surgical characteristics will be assessed with parametric testing (Student's t-test) for normally distributed data, and nonparametric testing (Mann-Whitney U test or Kruskal-Wallis test) for non-normally distributed data. These data will include pre-intervention Hb, post-intervention Hb, and duration of oral iron treatment (days).

Pre- and post-intervention Hb for the patient with IDA will be assessed by a paired t-test if data are normally distributed, and if data are not normally distributed then the data will be analyse using Wilcoxon ranked sum test.

Is there a statistically significant difference in pre and post intervention Hb in the IDA patients after adjusting for baseline haemoglobin?

The proposal is to use a mixed effect regression model. The final model will depend on the distribution of the outcome variable (post-intervention Hb). If the outcome is normally distributed, a linear mixed effect model will be used. If the outcome is not normally distributed, different approaches can be used depending on how skewed the outcome is e.g. Generalised Linear Mixed Effect Model

7. Study organisation and management

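### No parameter of the baseline-adjusted mixed model in section 5.11 is the pre-post Hb change, and versions that keep baseline as a covariate with default standard errors reject somewhat too often.

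*Combined protocol and SAP*

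**What the plan says.** The design (6.1) is a "Prospective interventional quasi-experimental pre-post study across multiple hospitals in South Africa", with no comparator. The primary outcome (5.2) is "DHb (pre-intervention Hb – post-intervention Hb"), a change within each child. The dataset (6.13) holds one pre-intervention and one post-intervention Hb for each child with IDA.

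Section 5.11 gives two analyses of this change:

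- **Paired test.** "Pre- and post-intervention Hb for the patient with IDA will be assessed by a paired t-test if data are normally distributed", with a Wilcoxon test otherwise.
- **Adjusted model.** The question is "Is there a statistically significant difference in pre and post intervention Hb in the IDA patients after adjusting for baseline haemoglobin", and the answer is "The proposal is to use a mixed effect regression model". The outcome is identified in the next sentence: "The final model will depend on the distribution of the outcome variable (post-intervention Hb"). If that variable is not normal, other approaches may be used according to its skewness, with a generalised linear mixed model as the example.

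For the adjusted model the section lists no fixed effects, random effect, grouping level, contrast or tested parameter. It does not say which of the two analyses decides.

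**The concern.** Adjusting post Hb for baseline Hb is sound in a two-arm trial because a group term carries the treatment effect. Here there is no group term, and the covariate is itself one half of the comparison. An analyst who fits the model as described gets p-values for an intercept and a slope, and neither says whether Hb rose.

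To answer the question the analyst must re-interpret the model after seeing data, and the available versions differ in error rate. The result could also disagree with the paired test, with no rule for which stands.

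A secondary matter is that the model family is to be chosen on the raw distribution of post Hb, not on DHb or on residuals. If that led to a non-identity link, the result would no longer be a change in g/dL.

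**Working it through.** **Inputs.** From the documents: one treated group; one pre and one post Hb per child; 44 expected IDA children (6.7 table); two-sided 0.05 ("Sample size = 176, power = 80%, two-tailed significance 0.05"); IDA numbers of 35, 53, 70 or 88 (5.10, "given an estimated sample size of 176 anaemic patients, if the incidence of IDA is unknown"). Assumed, because the documents give no values: Hb mean 10 g/dL, common SD σ = 1 g/dL, pre-post correlation ρ from 0.3 to 0.9, normal data.

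**1. The plan's own figures.** Solving the paired t-test for 80% power at n = 176 gives d = 0.21235, against 0.2123609 in the plan. For n = 35, 53, 70 and 88 it gives 0.487, 0.392, 0.340 and 0.302, against about 0.5, 0.4, 0.34 and 0.3. The power section reproduces, and it concerns paired tests, not the mixed model.

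**2. The model as written.** post = a + b × baseline + error.

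- a is the expected post Hb at baseline 0 g/dL.
- b is the pre-post association. Adding a constant to every post value leaves b and its SE unchanged, so its p-value is the same whether Hb rose or not.
- The mean change is not a parameter.

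With zero true change and n = 44, the test of a rejects in 99/95/75/31% of simulated trials at ρ = 0.3/0.5/0.7/0.9, and the test of b in 52/95/100/100%. These figures only show that the tests address other questions.

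**3. Versions that keep baseline as a covariate.** The true variance of the mean change is 2σ²(1−ρ)/n. If a model reports k times that variance, its type I error is about 2Φ(−1.96√k).

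- *Version A: DHb on sample-centred baseline, intercept read as the change.* Model variance σ²(1−ρ²)/n, so k = (1−ρ²)/[2(1−ρ)] = (1+ρ)/2.
- *Version B: pre and post stacked, with time, child intercept and baseline covariate.* The pooled baseline slope is (1+ρ)/2. The two residuals of a child then have covariance −σ²(1−ρ)²/4, which is negative, so the child variance is driven to zero. Average residual variance is σ²(1−ρ)(3+ρ)/4; the time effect has twice that over n, so k = (3+ρ)/4.

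Example at ρ = 0.5: A has k = 0.75 and 2Φ(−1.697) = 9.0%; B has k = 0.875 and 2Φ(−1.833) = 6.7%.

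| ρ | A, formula | A, simulated | B, formula | B, simulated | Paired t, simulated |
|---|---|---|---|---|---|
| 0.3 | 11.4% | 11.1% | 7.5% | 7.6% | 4.9% |
| 0.5 | 9.0% | 8.5% | 6.7% | 6.7% | 4.9% |
| 0.7 | 7.1% | 6.9% | 5.9% | 6.1% | 4.9% |
| 0.9 | 5.6% | 5.4% | 5.3% | 5.5% | 4.9% |

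Simulations used n = 44 and 40,000 trials per row; n = 35 and n = 88 give similar rates.

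Sensitivity:

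- With a post/pre SD ratio of 0.8, A is 13.4% at ρ = 0.5 and 11.7% at 0.7. With a ratio of 1.2 it is 6.8% and 5.4%.
- B depends on the reference distribution. A separate run at ρ = 0.3/0.5/0.7/0.85 gave 7.9/7.2/6.6/5.9% with normal critical values and 7.1/6.5/5.8/5.2% with t.

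**4. Versions that hold the level.**

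- Stacked data with time and a child intercept but no baseline covariate match the paired t-test: 4.8 to 5.2% over the settings simulated.
- Version A with the sampling error of the baseline mean added to the SE: the slope of DHb on baseline is 1−ρ, so the variance becomes σ²(1−ρ²)/n + (1−ρ)²σ²/n = 2σ²(1−ρ)/n, exactly the paired variance. Simulated: 4.5 to 5.0%.

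**The case against.** The strongest reply is that the primary result is already protected. The paired t-test comes first in 5.11, the power section is built on paired tests, and the mixed model is worded as a proposal. That stands, and it limits the severity.

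A reader might go further than the documents allow in four ways:

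- **That a mixed model cannot test the change, or that every workable version inflates error.** Step 4 shows two that hold 5%. One drops the adjustment the text asks for; the other keeps it but needs an SE the plan does not specify.
- **That the rejection rates in step 2 are error rates of the plan.** Section 5.11 does not propose the raw intercept or slope as its answer.
- **That the model fails because a child random effect is not identifiable.** With one post value per child it would not be, but 5.11 names no grouping level. A hospital intercept would be estimable in principle, though the 6.7 table expects only 4 to 12 IDA children at each of the eight hospitals listed.
- **That the generalised model would abandon the g/dL scale.** It is offered only as an example and no link is stated, so this is a risk to close off and not an established defect.

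What survives is the central point: following the text as written does not answer the question it poses. That is more than missing detail.

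**Conclusion.** The concern holds in limited form. That no coefficient of post Hb on baseline Hb is the mean change in a single group is algebra and needs no assumption.

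The inflation is modest and conditional. It is about 5.5 to 11% instead of 5% for versions that keep observed baseline and default SEs, under normality, n = 44, equal SDs and ρ between 0.9 and 0.3. It is near nominal at high correlation, and for version A it can exceed 11% if post Hb is less variable than pre Hb.

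This should be fixed, but it does not invalidate the primary comparison. Regression to the mean after selection on low Hb would affect every version, including the paired test; it is a separate matter and is not counted here.

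**What to change.** Rewrite the last paragraph of 5.11 so that it:

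- defines the model-based analysis on DHb with its mean as the estimand or, equivalently, on stacked pre and post Hb with a time effect, a child random intercept and no baseline covariate;
- reports the mean change in g/dL with a 95% CI, stating the sign convention (with DHb as pre minus post, a rise is negative);
- requires, if baseline adjustment is kept, that the SE of the contrast include the sampling error of the baseline mean;
- judges distributional fit on DHb or model residuals, not on raw post Hb, and stays on the g/dL scale;
- states that the paired analysis of DHb is primary and the model supportive.

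Optional: a hospital random intercept, Kenward-Roger degrees of freedom, a bootstrap interval if residuals are skewed, and a descriptive plot of DHb against the average of pre and post Hb.

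The cost is one paragraph and no new data. Intervals will be wider than from the default-SE adjusted versions by a factor of about 1/√k. Over ρ = 0.9 to 0.3 that is 1/√0.95 = 1.03 to 1/√0.65 = 1.24 for version A, and 1/√0.975 = 1.01 to 1/√0.825 = 1.10 for version B.

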6.2 Inclusion criteria

- Age > 6 months to <16 years
- Noncardiac surgery
- Elective surgery
- Anaemic as per WHO criteria¹

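### Section 5.11 picks the baseline-adjusted model from the raw distribution of post-intervention Hb, not from the model's residuals, and so allows an unneeded, unspecified switch after the outcome is seen

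*Combined protocol and SAP*

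**What the plan says.** Section 5.11 first gives a paired comparison of pre- and post-intervention Hb in the patients with iron deficiency anaemia (IDA). It then asks a further question: "Is there a statistically significant difference in pre and post intervention Hb in the IDA patients after adjusting for baseline haemoglobin". For this it proposes a mixed effect regression model, and states how the model is to be chosen: "The final model will depend on the distribution of the outcome variable (post-intervention Hb"). The two branches are:

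- "If the outcome is normally distributed, a linear mixed effect model will be used".
- If not, "different approaches can be used depending on how skewed the outcome is e.g. Generalised Linear Mixed Effect Model".

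The only normality method named, earlier in the same section, is for variables: "Normal distribution of continuous variables will be determined by Shapiro-Wilk testing". Neither section 5.11 nor any other part of the document mentions residuals, a distribution family, a link function or a skewness cut-off.

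Two other places bear on the point. The primary outcome in section 5.2 is "DHb (pre-intervention Hb – post-intervention Hb"), a difference in Hb. Entry is by low Hb: section 6.1 refers to "Those patients with a screening Hb meeting the criteria for anaemia" and section 6.2 lists "Anaemic as per WHO criteria".

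**The concern.** A linear mixed model makes its distributional assumption about the errors (and the random effects) given the covariates. Here baseline Hb is a covariate. Raw post-intervention Hb mixes two things: the shape of baseline Hb, which the model conditions on and about which it assumes nothing, and the shape of the errors, which is what matters. Selecting children for low Hb limits baseline Hb from above and tends to leave a tail to the left. That tail carries into post-intervention Hb and can fail a normality check although the linear model is right.

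At stake is the adjusted estimate. Once the check fails, the plan leaves the replacement open and lets the observed skewness of the outcome decide it. The usual GLMM families for a positive continuous outcome are right-skewed and normally use a log or inverse link. They suit a left-tailed outcome poorly, and their effect would not normally be a g/dL difference that can be set beside DHb.

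**Working it through.** The plan gives no figure for how often its rule would switch models, so there is none to reproduce on this point. The detectable effect in the power section (0.2123609 at 176 pairs) does reproduce (0.2123), but this issue does not touch it.

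**1. Inputs.** From the documents: 44 expected IDA patients (site table, section 6.7); IDA sample sizes of 35 to 88 (power table, section 5.10); entry on finger-prick Hb, followed by a laboratory blood count (section 6.12); ages from over 6 months to under 16 years (section 6.2). Assumed, because the documents do not give them: Shapiro-Wilk at 5% as the check; error SD 0.5–1.0 g/dL; slope of post- on pre-intervention Hb 0.5–1.0; Hb deficit below the cut-off gamma-distributed with mean 1.2 g/dL and shape 1 or 2.

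**2. Why the raw outcome misleads.** Write post = a + b·pre + e, with e independent of pre, and let γ denote skewness. Then

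γ(post) = [b³·SD(pre)³·γ(pre) + SD(e)³·γ(e)] / [b²·SD(pre)² + SD(e)²]^1.5.

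With normal errors γ(e) = 0, yet γ(post) is not zero unless γ(pre) is. For a gamma deficit of shape k below a sharp cut-off, SD(pre) = 1.2/√k and γ(pre) = −2/√k.

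- k=2, b=0.5, SD(e)=1.0: −1.414 × 0.424³ / (0.18 + 1)^1.5 = −0.08.
- k=2, b=0.7, SD(e)=0.5: −1.414 × 0.594³ / (0.353 + 0.25)^1.5 = −0.63.
- k=1, b=1.0, SD(e)=0.5: −2 × 1.2³ / (1.44 + 0.25)^1.5 = −1.57.

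The errors, on which the linear model depends, have skewness 0 in all three.

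**3. How often the check fails when the linear model is correct.** Simulated trials with normal errors, 1000–3000 per cell. Shapiro-Wilk was applied to raw post-intervention Hb and to residuals from its regression on baseline.

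| Baseline Hb | Raw fails, n=44 | Raw fails, n=88 |
|---|---|---|
| Normal | 4–5% | about 5% |
| Normal, truncated at one threshold or age-mixed thresholds | 7–30% | 10–52% |
| Sharp cut-off minus gamma deficit, shape 2 | 6–46% | 6–74% |
| Sharp cut-off minus gamma deficit, shape 1 | 11–83% | 17–99% |
| Shape 2, cut-off blurred (finger-prick/laboratory SD 0.7 g/dL, three cut-offs) | 6–15% | up to 27% |
| Shape 1, blurred in the same way | 9–44% | up to 73% |

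Residuals fail in about 4–7% throughout. In the middle example of step 2, at n=44, the raw check fails in 27% of trials and the residual check in 5%. With a smaller disagreement of 0.5 g/dL and cut-offs of 11–12 g/dL, at slope 0.7 and SD 0.5, the raw check fails in 11–42% at n=44 and 21–71% at n=88. Over the whole blurred grid the range at n=44 is roughly 5–57%; the upper end belongs to shape 1.

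**4. What is lost if skewed errors go unnoticed.** With right-skewed gamma errors of shape 2, residuals fail Shapiro-Wilk in 87–89% of trials at n=44 and in over 99% at n=88. The ordinary linear-model 95% interval for mean post-intervention Hb at the mean baseline nevertheless covers about 93–96%.

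The simulations used ordinary regression without a random effect, since section 5.11 does not name one.

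**The case against.** Several points on the other side stand.

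- A reader might infer that the primary analysis is compromised. It is not: section 5.11 gives pre- and post-intervention Hb its own paired test, and the mixed model answers an additional question. A switch there does not replace the paired result.
- A reader might infer that the rule is equally harmful in the other direction, because skewed errors can hide behind a normal-looking outcome. They can, but step 4 shows that the linear interval barely suffers. A missed diagnostic is not a wrong inference.
- A reader might infer that the fallback is necessarily a ratio of Hb. Section 5.11 names no family or link, and an identity link would keep g/dL. The documented fault is that the scale is left open.
- The cut-off on baseline Hb is not sharp. Entry is by finger-prick, whereas section 6.13 lists pre-intervention Hb separately from the finger-prick value and section 6.12 has a laboratory count drawn after screening. Thresholds may also differ across so wide an age range. Allowing for this lowers the upper end at n=44 from about 83–85% to about 57%, and lower still with larger disagreement. With a normal baseline the excess disappears.
- Section 5.11 does not say that Shapiro-Wilk at 5% triggers the switch. The test is named for continuous variables in general, and the model text speaks only of how skewed the outcome is. The percentages depend on that reading.

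What does not fall is the rule itself. It directs the analyst to the wrong quantity, and nothing else in the document adds a residual check or fixes the alternative.

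**Conclusion.** The concern holds for the baseline-adjusted analysis only. As written, section 5.11 can discard a correct linear mixed model because children were selected on low Hb, and put in its place a model whose form and scale are settled after the outcome has been seen. Under the stated assumptions this would happen in roughly 5–57% of trials at n=44, against about 5% if residuals were checked; at n=88 the upper ends are higher. The figures are illustrative: they rest on assumed SDs, slopes, baseline shapes and a 5% Shapiro-Wilk trigger. The direction needs only a non-normal baseline, which the entry criterion makes likely. The documents do not support the wider claims that the DHb comparison is invalid, that the adjusted effect will certainly leave the g/dL scale, or that unseen residual skew damages the linear estimate. Sample size and power are unaffected.

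**What to change.** In section 5.11, delete the choice of model by the distribution or skewness of post-intervention Hb, and replace it with wording such as:

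> The adjusted analysis is a linear mixed model for Hb in g/dL, whatever the marginal distribution of post-intervention Hb. Residuals are inspected graphically. If they are clearly non-normal, the same estimate is kept and a robust or bootstrap 95% CI that respects the model's clustering is reported as a sensitivity analysis.

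This keeps the adjusted effect on the scale of DHb and removes a choice made after the outcome is seen. A robust and a bootstrap interval would serve equally well; name one in advance, and name the random effect so that the clustering is defined. The cost is a change of wording and at most one extra interval, with no new data or patients.

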7.1 Study steering committee

The Steering Committee will be chaired by HM. The study management team will be appointed by the Steering Committee and led by HM. The duties of this team will include administration of all project tasks, communication between project partners (including funders, Steering Committee members, local coordinators, etc.), data collation and management and preparation of reports for individual study sites. The Steering Committee is responsible for the scientific conduct and consistency of the project. The Steering Committee will ensure communication between the funder(s), study management team and co-ordinators as necessary.

7.2 Patient advocate

Patient advocate(s) will be appointed who will advise the Steering Committee on possible protocol amendments if required, based on patient concerns regarding delivery of the study or communication of the study.

7.3 Local co-ordinators

Local co-ordinators in individual institutions will have the following responsibilities:

- Provide leadership for the study in their institution
- Ensure all relevant regulatory and ethics approvals are in place for their institution
- Ensure adequate training of all relevant staff prior to data collection
- Supervise daily data collection and site recruitment and follow up management
- Act as guarantor for the integrity and quality of data collected
- Ensure timely completion of electronic CRFs
- Communicate with the relevant national co-ordinator

7.4 Training of investigators

Training will be done via online virtual training sessions. Each study site will be required to complete an online questionnaire as part of the site initiation, prior to starting data collection.

8 Data management and ownership

On behalf of the Steering Committee, the Department of Anaesthesia and Perioperative Medicine, Groote Schuur Hospital and University of Cape Town will act as custodian of the data. The Steering committee will retain the right to use all pooled data for scientific and other purposes. Members of the SAPSOS-2 study group will have the right to access the pooled data for research purposes provided the research proposal has been reviewed and deemed appropriate by the Steering Committee. The primary consideration for such decisions will be the quality and validity of any proposed analysis. Only summary data will be presented publicly, and all institutions will be anonymised except in the individualised report provided to each institution at the end of the study. Individual patient data provided by participating sites remain the property of the respective institutions.

9 Publication plan

Data will be presented and disseminated in a timely manner. The Steering Committee will appoint a writing committee to draft the scientific report(s) of this investigation. The group will be known as 'The SAPSOS-2 Investigators'. Participation and authorship opportunities will be based on contribution to the primary study. On request, hospitals will be provided with an individual report allowing comparison of their individual hospital's summary data to that of their national cohort. In line with the principles of data preservation and sharing, the Steering Committee will, after publication of the overall dataset, consider all reasonable requests to make the dataset available in whole or part for secondary analyses and scientific publication. The Steering Committee will consider the scientific validity and the possible effect on the anonymity of participating hospitals prior to granting any such requests. Where appropriate, a prior written agreement will set out the terms of such collaborations. The Steering Committee will consider proposals for secondary analyses on the basis of the scientific quality of the proposal. The Steering Committee must approve the final version of all manuscripts prior to submission, whether they relate to part or all of the SAPSOS-2 dataset.

10 Management of premature termination of the trial
